Title: External Tibia Torsion and Passive Muscle Stiffness of Quadriceps as Two Important Contributors of Joint Loading during Walking in People With Knee Osteoarthritis

NCT number: NCT03628508

Document date: 27-Jul-2020

Study Protocol

Excessive mechanical loading on the knee joint is the main cause for the onset and progression of knee osteoarthritis (OA), a degenerative disease causing pain and functional disabilities in the elder. Malalignment of the lower limb and muscle insufficiency are the contributing factors that might induce excessive mechanical loading during gait on knee joint. The inter-action of joint alignment, muscle properties and joint loading on gait has not been well explored.

Comprehensive understanding of knee joint alignment and muscle properties could enhance knowledge of pathogenesis of knee osteoarthritis and provide scientific evidence for the prevention and rehabilitation of knee osteoarthritis.

Taken advantage of gait analysis system, dynamic joint loading distribution can be indirectly presented as external knee adduction moment (KAM), revealing biomechanical perspectives of knee joint during gait. Increase in KAM was reported in individuals with knee osteoarthritis, and it is associated with pain and disease progression. Such information is important for prevention and rehabilitation for knee osteoarthritis. Increase in muscle tension can induce excessive compressive loading on the knee joint. Passive tension is of tremendous importance in skeletal muscle function, attributing to total tension production in lengthening conditions and affecting joint range of motion as well as stability. Knee osteoarthritis possibly changes both muscular tissue and connective tissue of skeletal muscles which is muscle fiber types specific. In view of the different muscle fibre types in the muscle heads of the quadriceps femoris, it is possible that alteration in passive muscle tension is different in the muscle heads of the quadriceps. We are interested in investigating quadriceps passive tension of individuals muscle heads with Supersonic shearwave elastography, a relatively new technology for measuring shear modulus (an index of muscle tension). Exploration on possible increase in passive muscle tension of individual muscle heads of the quadriceps in individuals with knee osteoarthritis would shed light on the influence of passive muscle tension on pain and joint loading during gait.

Malalignment, such as varus deformities are commonly seen in individuals with knee osteoarthritis. Varus deformity is associated with pain and dysfunctions in individuals with medial knee osteoarthritis. More recently, torsional malalignment is also recognized in knee osteoarthritis. External tibial rotation decreases gradually with the progression of osteoarthritis. Nevertheless, there lacks solid evidence indicate the relationship between torsional alignment

and joint force transmission. Since malalignment plays a vital role in the determination of joint mechanical loading distribution, to clarify the attribution of different components of knee alignment could be beneficial to prognosis evaluation of osteoarthritis progression and function limitation.

The aim of this study is to investigate the inter-relationship between medial knee joint loading, knee alignment and muscle properties. The specific objectives of this study are: (1) to investigate the correlation between hip abduction strength and knee joint loading in individuals with medial knee osteoarthritis; (2) to explore passive tension alteration of superficial heads of quadriceps femoris and its link to joint loading and self-perceived pain; (3) to examine the relationship between knee alignment and joint loading as well as quadriceps passive tension.

Statistical analysis plan

Pearson's r test is used to identify the strength of correlation between the tested parameters. In the analysis of preliminary results, these correlations are assessed by Spearman's rho test. Single regression is used to examine predictability of the two parameters. The difference of parameters between elder with and without knee osteoarthritis is compared by independent t test.

Association between alignment parameters and KAM is assessed by linear multiple regression test.

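### The plan gives no alignment-adjusted estimate for hip abduction strength, so it cannot separate the contribution of strength to knee loading from that of alignment

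*Combined protocol and SAP*

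**What the plan says.** The Study Protocol background names two sources of excess loading together: "Malalignment of the lower limb and muscle insufficiency are the contributing factors that might induce excessive mechanical loading during gait on knee joint". It later adds that "malalignment plays a vital role in the determination of joint mechanical loading distribution". The overall aim is "to investigate the inter-relationship between medial knee joint loading, knee alignment and muscle properties". Specific objective (1) is narrower: "to investigate the correlation between hip abduction strength and knee joint loading in individuals with medial knee osteoarthritis". Alignment enters under objective (3), which relates it to loading and to quadriceps passive tension. KAM is introduced in the background as an indirect measure of joint loading.

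The Statistical analysis plan lists methods without assigning them to numbered objectives:

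- For correlations: "Pearson's r test is used to identify the strength of correlation between the tested parameters".
- For the preliminary results, Spearman's rho takes the place of Pearson's r.
- For prediction, a regression with a single predictor is used.
- For alignment: "Association between alignment parameters and KAM is assessed by linear multiple regression test".

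It also gives an independent t test for comparing elders with and without osteoarthritis. The documents state no sample size, significance level, power, expected correlation or number of alignment parameters. They do not say how hip strength and alignment are expected to relate.

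**The concern.** Objective 1 is worded as a correlation, and the listed methods that fit it (Pearson's r, Spearman's rho for preliminary results, single regression) each take two variables. The only model with several predictors of KAM is described for alignment parameters, and hip abduction strength is not among its terms. No planned analysis therefore puts strength and alignment into one model of loading, although the aim and the background concern both.

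What is at stake is interpretation. If weaker abductors tend to go with worse alignment, a crude strength-KAM correlation carries some of the alignment effect. If stronger abductors go with worse alignment, the crude correlation can hide a link that is present at fixed alignment. In either case a statement that muscle makes its own contribution to loading would have no analysis behind it.

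**Working it through.** The plan has no figure to reproduce. All correlations and sample sizes below are assumptions used for illustration, and tests are taken as two-sided at 5%.

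**Notation.** x = hip abduction strength, y = KAM, z = one alignment parameter, scored so that higher values go with higher KAM.

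Partial correlation of x and y given z:

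r(xy.z) = (r_xy − r_xz·r_yz) / √[(1 − r_xz²)(1 − r_yz²)]

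**Step 1: how far a crude r can differ from the adjusted one.** Take r_yz = 0.5 and crude r_xy = −0.15.

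- r_xz = −0.3: (−0.15 + 0.15) / √(0.91 × 0.75) = 0.
- r_xz = +0.3: (−0.15 − 0.15) / √(0.91 × 0.75) = −0.30 / 0.826 = −0.36.

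The same crude result is compatible with no link at fixed alignment and with a moderate one.

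**Step 2: how often the crude test is significant when strength has no link to KAM given alignment.** The crude correlation is then r_xz·r_yz. With −0.3 and 0.5 it is −0.15. By the Fisher z approximation the crude test rejects about 12%, 18% and 32% of the time at n = 30, 50 and 100. Simulation with exact t tests agrees: at n = 50, about 18% for the crude test and 5% for the adjusted one. With r_xz = 0 the crude rate stays at 5%.

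These rejections are not errors about the crude correlation, which really is −0.15. They mislead only if read as a separate contribution of strength.

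**Step 3: effect on power.** Power ≈ Φ(atanh|r|·√(n − 3 − k) − 1.96) plus the small opposite tail, with k = 0 for the crude r and k = 1 for one alignment covariate. Take crude r_xy = −0.3, r_yz = 0.5, n = 50. Crude power is 56%, and the n for 80% power is 85.

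| Assumed r_xz | Partial r | Adjusted power, n = 50 | n for 80% power |
|---|---|---|---|
| +0.3 | −0.545 | 98.5% | 26 |
| 0 | −0.346 | 69% | 65 |
| −0.3 | −0.182 | 24% | 237 |
| −0.5 | −0.067 | 7% | 1765 |

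Adjustment raises power in the first two rows and lowers it in the last two. Any gain under r_xz = 0 also depends on how much KAM variance alignment explains. At n = 50, adjusted power is 60%, 69% and 86% for r_yz of 0.3, 0.5 and 0.7, against 56% crude. The documents describe the importance of alignment in words only, so nothing in them selects a row.

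**The case against.** The strongest reply is that the planned method answers the stated question. Objective 1 asks for a correlation, and a crude r estimates exactly that. The objective claims no independent, adjusted or causal effect, and making a partial correlation the objective 1 result would replace its estimand. This stands, and it is why the crude r should stay as the objective 1 answer.

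A reader might also infer that leaving alignment out necessarily costs power and at the same time mixes the two contributors. The documents do not support that. The two effects rest on different values of an unstated correlation. If strength and alignment are uncorrelated, there can be a power loss but no mixing. If weaker abductors go with worse alignment, there is mixing, and the crude test may reject more often than the adjusted one (56% against 24% in the third row above).

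Two further cautions hold. That objective 1 will be analysed only by two-variable methods is a strong inference from its wording, because the plan maps no test to an objective. The population of the KAM regression is also not named, so whether it uses the same participants as objective 1 is an assumption.

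None of this removes the gap against the overall aim, which covers alignment and muscle together.

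**Conclusion.** The point holds as a gap between the aim and the listed analyses, not as an error in the objective 1 test. The plan names alignment and muscle as contributors to loading and sets out to study their inter-relationship, but it lists no analysis that gives a hip-strength estimate at fixed alignment.

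The size is conditional. With an assumed alignment-KAM correlation of 0.5 and strength-alignment correlations of ±0.3, a crude r of −0.15 can stand for a partial r anywhere from 0 to −0.36. The effect on power may be up or down, and no power figure belongs to this study. Because the remedy uses measures the plan already provides for, the change is worth making as a low-cost improvement.

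**What to change.** Keep the crude correlation as the literal answer to objective 1. In the osteoarthritis participants with both measures, also fit the planned multiple regression of KAM with hip abduction strength added to the alignment parameters. Report the strength slope and partial correlation, each with a 95% confidence interval, beside the crude r. State that any conclusion about a separate contribution of muscle will rest on the adjusted estimate. The same text should say which test serves which objective, and which participants and alignment parameters enter the regression.

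No new measurement is needed beyond those the objectives already require. The statistical cost is one degree of freedom per term in the model; the total is unknown because the number of alignment parameters is not stated. The adjusted coefficient must be read as conditional on alignment, and its interval may be wider or narrower than the crude one.

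### The comparison of older people with and without knee OA is an unadjusted t test with no matching stated, so any age, sex or BMI imbalance would enter the difference; adjusted results should stand beside it and beside the bivariate correlations.

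*Combined protocol and SAP*

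**What the plan says.** The Statistical analysis plan is five sentences. For relationships: "Pearson's r test is used to identify the strength of correlation between the tested parameters", with Spearman's rho used for preliminary results. For prediction: "Single regression is used to examine predictability of the two parameters". For the group contrast: "The difference of parameters between elder with and without knee osteoarthritis is compared by independent t test". The only multivariable model is the last: "Association between alignment parameters and KAM is assessed by linear multiple regression test".

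No covariate is named for the t test, the correlations or the single regression. Sex, BMI, body mass and height appear nowhere in the document, and age appears only in the description of the participants as older people. No matching, restriction or stratification of the two groups is stated, and no normalisation of the knee adduction moment (KAM) or of hip strength.

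The title goes further than association for two variables: "External Tibia Torsion and Passive Muscle Stiffness of Quadriceps as Two Important Contributors of Joint Loading". The first specific objective in the Study Protocol is more modest: "to investigate the correlation between hip abduction strength and knee joint loading in individuals with medial knee osteoarthritis".

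**The concern.** People with and without knee OA cannot be randomised to their group, so nothing in the design as described balances them. If the groups differ in age, sex or BMI, an independent t test attributes to OA whatever part of the difference those factors carry. A larger sample does not help: the bias stays the same size and is declared significant more often.

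The same gap affects the pairwise analyses, in particular quadriceps stiffness with KAM and with pain. An unadjusted correlation or single regression cannot separate a link between two measurements from the part that both share with age, sex or body size. This matters because the title calls stiffness a contributor to loading, and the Study Protocol hopes to learn about its influence on pain and loading.

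**Working it through.** The documents give no sample size, alpha, effect size or SD, so there is no figure of the plan's own to reproduce. All inputs below are assumptions, with two-sided alpha 0.05.

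**1. Group comparison.** Suppose that OA makes no difference once a covariate is held fixed, the groups differ by *a* SD on that covariate, and the outcome changes by *s* SD per SD of it. The t test then targets a spurious standardised difference d = a x s. With n = 30 per group (58 df) the noncentrality is d x sqrt(n/2) = d x 3.873, and the rejection rate follows from the noncentral t distribution. The last two columns are simulated, with 20,000 studies per row.

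| a x s | d | Noncentrality | t test, exact | t test, simulated | ANCOVA, simulated |
|---|---|---|---|---|---|
| 0.2 x 0.2 | 0.04 | 0.155 | 5.3% | 5.4% | 5.2% |
| 0.5 x 0.3 | 0.15 | 0.581 | 8.8% | 8.7% | 4.9% |
| 0.5 x 0.5 | 0.25 | 0.968 | 15.9% | 15.8% | 5.2% |

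In the third row, a normal approximation gives 12.4%, 16.2% and 24.0% at 20, 30 and 50 per group, so the problem grows with sample size. ANCOVA holds 5% here because the covariate that matters is in the model and acts linearly.

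**2. Hip strength and KAM.** Suppose that both correlate b with body size and have no other link. The raw correlation is then b x b: 0.09 at b = 0.3, 0.25 at b = 0.5 and 0.36 at b = 0.6. By Fisher z with SE 1/sqrt(n - 3), it is significant at n = 50 in 9.5%, 42% and 73% of studies. This applies only if neither variable is normalised and both scale with body size.

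If both are divided by body mass, the correlation becomes (2,000,000 simulated subjects):

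| b (raw r) | Outcome CV 20%, mass CV 10 / 15 / 20% | Outcome CV 30%, mass CV 10 / 15 / 20% |
|---|---|---|
| 0.3 (0.09) | 0.05 / 0.20 / 0.41 | 0.00 / 0.05 / 0.16 |
| 0.5 (0.25) | 0.00 / 0.09 / 0.30 | 0.04 / 0.00 / 0.05 |
| 0.6 (0.36) | 0.02 / 0.04 / 0.25 | 0.11 / 0.02 / 0.01 |

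Where the raw distortion is large (b = 0.5 or 0.6), normalisation brings it to 0.11 or less in five of six cells. It fails at mass CV 20% with outcome CV 20%. At b = 0.3, where there was little to remove, it raises the correlation in three of six cells.

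**3. Power cost of adjustment.** For a true r of 0.4, Fisher z = 0.4236, with SE 1/sqrt(n - 3 - k) for k covariates.
- n = 30: 0.4236 x sqrt(27) = 2.20, power 60%. With k = 3, 0.4236 x sqrt(24) = 2.08, power 55%.
- n = 50: 0.4236 x sqrt(47) = 2.90, power 83%. With k = 3, 0.4236 x sqrt(44) = 2.81, power 80%.

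**The case against.** The strongest reply is that no bias has been shown. Every input above is assumed, the low end of the range is harmless, and the groups may in fact be comparable. That stands. A reader might infer that the OA versus non-OA difference is biased; the documents support only that the plan as written gives no protection if an imbalance exists.

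A second reply is that the first objective asks for a correlation within people with medial knee OA, and Pearson's r estimates exactly that. This also stands. A reader might infer that the hip strength result is spurious or causally overclaimed. The title's contributor wording does not cover hip strength, and the background speaks only of muscle insufficiency in general ("Malalignment of the lower limb and muscle insufficiency are the contributing factors that might induce excessive mechanical loading during gait on knee joint"). The body-size concern there rests on two conditions that the documents do not establish. Nor do the figures support a general claim that dividing by mass is unsafe: it works in many plausible settings and fails in some.

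A third reply is that torsion and KAM fall under the multiple regression, not the pairwise tests. Correct. That sentence lists no predictor beyond alignment but does not exclude others, so it does not show that the model is unadjusted.

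Finally, a reader might suspect that correlations pooled over both groups would pick up OA status itself. The text does not say that groups are pooled, so this is not part of the point.

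What remains is the unadjusted t test between non-randomised groups and the pairwise analyses of stiffness. For both, the plan states no design or analysis safeguard.

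**Conclusion.** The concern holds in a limited form. Followed as written, the plan leaves any age, sex or BMI imbalance in the group difference for every parameter that varies with those factors; for muscle stiffness, that dependence is itself an assumption. With 30 per group the illustrated effect runs from negligible (d = 0.04, 5% rejection) to material (d = 0.25, 16%), against about 5% with ANCOVA. The true size cannot be derived from the documents.

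The pairwise correlations and single regressions share the gap. For hip strength and KAM it is conditional and carries less weight.

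A reader might also infer that adjusted results would justify calling torsion or stiffness contributors to loading. They would not: adjusting observational data for a few covariates does not establish cause. This is an inexpensive improvement that should be made, not a flaw that invalidates the study.

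**What to change.** - **Group comparison:** keep the t test and pre-specify beside it an ANCOVA adjusted for age and sex. Report a further model adding BMI separately. The Study Protocol treats excess loading as the principal cause of OA, so BMI may lie on the path between loading and OA, and adjusting for it changes the question.
- **Correlations and single regressions**, including stiffness with KAM and with pain: report a partial correlation or regression adjusted for age, sex and body mass beside the unadjusted result.
- **Design facts:** state whether the groups were matched or restricted, and whether KAM and hip strength are normalised and how.
- **Wording:** describe every result, adjusted or not, as an association, and hold back contributor or influence language.

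The cost is SAP wording and minor analysis work. For a true r of 0.4, three covariates take power from 60% to 55% at n = 30 and from 83% to 80% at n = 50. Adjusting KAM for body mass asks a different question from absolute loading, which is a further reason to keep the unadjusted result. The change depends on age, sex and body mass (and height, for BMI) having been recorded, which the documents do not say. If they were not, the adjusted analyses cannot be run and that limitation should be reported.

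### Does the lack of a primary test, significance level and multiplicity rule undermine the two contributors named in the title?

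*Combined protocol and SAP*

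**What the plan says.** The Statistical analysis plan is five sentences long. For correlations it says "Pearson's r test is used to identify the strength of correlation between the tested parameters". Spearman's rho is reserved for an interim stage, in the sentence that begins "In the analysis of preliminary results, these correlations are assessed by". Simple regression is planned for pairs of parameters. For group differences, "The difference of parameters between elder with and without knee osteoarthritis is compared by independent t test". For alignment, the plan is "Association between alignment parameters and KAM is assessed by linear multiple regression test".

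The Study Protocol lists three objectives without ranking them. The first relates hip abductor strength to loading and is confined to people with medial disease. The second is "to explore passive tension alteration of superficial heads of quadriceps femoris and its link to joint loading and self-perceived pain". The third links alignment with loading and with muscle tension.

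The title describes external tibial torsion and passive quadriceps stiffness "as Two Important Contributors of Joint Loading during Walking in People With Knee Osteoarthritis".

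Neither part gives a significance level, sidedness, sample size, primary test, KAM summary, list of alignment parameters, number of heads or multiplicity approach. Only objective 1 names its population.

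**The concern.** The title reads like a finding, and the plan contains no rule for reaching it. Four features make that look risky.

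- Stiffness is measured in more than one head, and the Study Protocol expects that the heads may differ. The stiffness factor therefore has several chances to show a link with loading.
- Two correlation methods appear for the same relations.
- A comparison group without osteoarthritis exists, and the plan does not say whether it enters the correlations for objectives 2 and 3.
- Hip abduction strength is the first objective but is absent from the title, so a reader may wonder how the two named factors were chosen.

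If a factor could be declared a contributor on any favourable result, the error rate of the claim would be uncontrolled, and a reader could not separate a planned result from a selected one.

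**Working it through.** The documents give no alpha, counts or sample size, so there is no figure of the plan's own to reproduce. Everything below is illustrative.

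**Assumed inputs.** Two-sided alpha 0.05 (0.01 as a sensitivity value); h = 2 to 3 heads; a = 2 to 3 alignment parameters; no true associations unless stated. The objectives speak of heads in the plural, and the background discusses varus and torsional malalignment, hence at least two of each.

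**1. Title factors: torsion plus h heads, at least one false positive.** With independent tests, 1 − 0.95^(1+h):
- h = 2: 1 − 0.95^3 = 0.143
- h = 3: 1 − 0.95^4 = 0.185
- at alpha 0.01: 1 − 0.99^3 = 0.030 and 1 − 0.99^4 = 0.039

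Simulation (20,000 replicates per scenario, normal data, n = 30 and 50, between-head correlation 0.5 to 0.9, torsion tested in a multiple regression) gives 0.117 to 0.171 at alpha 0.05.

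**2. Both title factors false.** 0.05 × (1 − 0.95^h) = 0.05 × 0.0975 = 0.0049 for h = 2, and 0.05 × 0.1426 = 0.0071 for h = 3. Simulated with correlated heads: 0.003 to 0.007.

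**3. Torsion real, stiffness not.** The heads alone give 1 − 0.95^2 = 0.0975 to 1 − 0.95^3 = 0.143 if independent, and 0.071 to 0.127 if correlated.

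**4. How the family is drawn.** Loading tests only (hip strength, h heads, a alignment terms) number 5 to 7: 1 − 0.95^5 = 0.226 to 1 − 0.95^7 = 0.302. Counting every relation in the objectives, m = 1 + 3h + a(1 + h):
- h = 2, a = 2: m = 1 + 6 + 6 = 13, and 1 − 0.95^13 = 0.487
- h = 3, a = 3: m = 1 + 9 + 12 = 22, and 1 − 0.95^22 = 0.677

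With equicorrelated tests (0.3 to 0.7) the second range falls to 0.24 to 0.57. So the answer runs from under 1% to about 68%, depending on which claim and which family one chooses.

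**5. Cost of formal control.** With two primary tests under Holm, the first step is at 0.05/2 = 0.025. Power for a correlation of 0.4 is Φ(atanh(0.4) × √(n − 3) − z), with atanh(0.4) = 0.4236 and z = 1.960 or 2.241:

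| n (assumed) | at 0.05 | at 0.025 | loss |
|---|---|---|---|
| 30 | 0.595 | 0.484 | 0.111 |
| 50 | 0.828 | 0.746 | 0.082 |
| 80 | 0.961 | 0.930 | 0.031 |

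For the torsion coefficient (partial correlation 0.4, simulated, two alignment parameters) the fall is 0.586 to 0.471 at n = 30, a loss of 0.115, and 0.830 to 0.747 at n = 50, a loss of 0.083.

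**6. Reading the text against the concern.**
- *Decision rule.* No sentence says that one significant head makes stiffness a contributor. That rule has to be supplied by the reader.
- *Method.* Spearman is tied to the preliminary results and Pearson covers the rest. Reporting the better of the two would give roughly 6% to 7% in place of 5%, but it would depart from the plan.
- *Adjustment.* The alignment model is a multiple regression, so torsion is already adjusted for the other alignment parameters.
- *Population.* The title restricts the claim to people with knee osteoarthritis, which points to the natural population for the loading correlations.
- *Status.* Objective 2 is openly exploratory, the general aim is to study inter-relationships, and no hypothesis is stated.

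**The case for a change.** The strongest case for a change is that the plan never declares itself exploratory, while its title asserts a conclusion. If torsion truly affects loading, the stiffness half of that conclusion still carries a 7% to 14% false-positive risk instead of 5%. The change would need wording only, and it could be met simply by labelling all tests exploratory and reporting each with a confidence interval.

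Population also matters. With no association inside either group, but with osteoarthritis participants higher by an assumed 0.5 to 0.8 SD on both KAM and stiffness, pooling the groups yields a significant correlation in 7% to 18% of studies (30 per group) or 9% to 28% (50 per group).

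Part of this stands. The omissions are genuine, nothing marks them as redacted, and a fuller plan would be easier to read. The title is stronger than the objectives beneath it. But the pooling figures describe a choice that the plan does not make and that the title argues against. They also rest on an assumed stiffness difference, which the protocol treats only as possible. Selection of the two factors from preliminary results is likewise only a possibility; nothing in the documents shows it.

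Naming two primary tests is not neutral either. It would infer the sponsor's priorities from the title, push the first-listed objective down, and reduce the heads to one or an average although the scientific interest lies in their differences. It would still leave no model containing torsion and stiffness together.

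**Conclusion.** No change follows. The unstated level, KAM summary, parameter list and population are missing detail that an analyst would fill conventionally, and no rule in the plan produces a wrong result. Whether to impose family-wise control or to treat the whole study as exploratory is a choice on which reasonable statisticians differ for a correlational study of this kind.

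Under an assumed two-sided 5% level with 2 to 3 heads, the joint false claim in the title has a probability of 0.5% to 0.7% when nothing is true. The more relevant excess, a false stiffness claim beside a real torsion effect, is 7% to 13% with correlated heads. Larger figures need a wider family or selection after seeing the results. Against this stands a loss of about 8 to 12 percentage points of power at 30 to 50 participants for a correlation of 0.4.

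All of these figures rest on assumed alpha, counts, correlations and sample sizes. The judgement would differ if the plan stated that any single significant head suffices to call stiffness a contributor; it does not.

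### Do the association tests for torsion and knee loading need a stated population and a severity term?

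*Combined protocol and SAP*

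**What the plan says.** The section headed Statistical analysis plan names these methods:

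- Correlation: "Pearson's r test is used to identify the strength of correlation between the tested parameters", with Spearman's rho for preliminary results.
- One-predictor regression: "Single regression is used to examine predictability of the two parameters".
- Alignment and loading: "Association between alignment parameters and KAM is assessed by linear multiple regression test".
- Group comparison: "The difference of parameters between elder with and without knee osteoarthritis is compared by independent t test".

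The section does not assign tests to objectives, name an analysis set for each test, or list covariates beyond the alignment parameters. In the Study Protocol section, objective 1 is restricted to medial knee OA, while objectives 2 and 3 name no population. The study title refers to people with knee OA.

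The background makes two statements about progression. On torsion: "External tibial rotation decreases gradually with the progression of osteoarthritis". On loading: "Increase in KAM was reported in individuals with knee osteoarthritis, and it is associated with pain and disease progression".

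**The concern.** Two features look like gaps.

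First, controls are measured, but the plan does not say whether they enter the correlations and regressions. If they were pooled with no OA term, any two variables that both differ between groups would correlate even with no association within OA.

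Second, even with OA participants only, the protocol's own background gives torsion and KAM opposite links to progression. If participants differ in severity at the visit, rotation and KAM could correlate negatively with no association at a given severity. Correlation and one-predictor regression cannot separate these, and the multiple regression names only alignment terms.

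At stake is interpretation. The title calls torsion a contributor to loading, and the background hopes that "to clarify the attribution of different components of knee alignment could be beneficial to prognosis evaluation of osteoarthritis progression and function limitation". A coefficient produced by shared dependence on severity would not support that wording.

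**Working it through.** **Inputs.** The documents give no sample size, standard deviation, effect size or significance level, so there is no planned figure to reproduce. Everything below assumes correlations with severity of size *a*, negative for rotation and positive for KAM, and a two-sided 5% test.

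**1. Which population?** The title is about people with OA. Objective 1 is limited to OA. The rationale for measuring passive tension says that a possible increase "in individuals with knee osteoarthritis would shed light on the influence of passive muscle tension on pain and joint loading during gait". Controls appear only in the t-test sentence, where OA status is the grouping factor; that test suits the part of objective 2 on whether passive tension is altered. Nothing says that the groups are pooled for the association tests. Read together, these passages point to OA-only association analyses.

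**2. Severity as a common cause (OA only, no association at a given severity).** The marginal correlation is r = (-a)(a) = -a². By the Fisher z approximation, the chance of p<0.05 is Φ(z - 1.96) + Φ(-z - 1.96), with z = atanh(|r|)·√(N-3). For a = 0.4 and N = 50: r = -0.16, z = 0.1614 × √47 = 1.106, chance = Φ(-0.854) + Φ(-3.066) = 0.198.

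| a | r | N=30 | N=50 | N=100 |
|---|---|---|---|---|
| 0.2 | -0.04 | 5.5% | 5.9% | 6.8% |
| 0.3 | -0.09 | 7.6% | 9.5% | 14.4% |
| 0.4 | -0.16 | 13.4% | 19.8% | 35.6% |
| 0.5 | -0.25 | 26.4% | 41.7% | 71.1% |

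Simulation with 20,000 data sets per setting, run for a = 0.3 and above, agrees. With severity in the model the rate returns to about 5%. These figures are for a two-variable correlation; the multiple regression named for alignment and KAM was not simulated, and its other terms may absorb part of the effect.

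**3. Severity as a consequence of both (true torsion-KAM correlation zero).** The unadjusted r is now correct. The partial correlation given severity is [0 - (-a)(a)]/(1 - a²) = a²/(1 - a²):

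- a = 0.2: 0.04/0.96 = +0.04
- a = 0.3: 0.09/0.91 = +0.10
- a = 0.4: 0.16/0.84 = +0.19
- a = 0.5: 0.25/0.75 = +0.33

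Adjustment does at least as much harm here as omission does in step 2, because a²/(1 - a²) exceeds a².

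**4. Severity downstream of loading only.** The Study Protocol's opening paragraph says malalignment may raise loading, and that loading drives onset and progression. Suppose the true torsion-KAM correlation is ρ and KAM correlates b with severity, so torsion correlates ρb with it. The partial correlation is (ρ - ρb²)/√[(1 - ρ²b²)(1 - b²)] = ρ·√(1 - b²)/√(1 - ρ²b²). As ρ²b² < b², this is smaller in absolute value than ρ: adjustment dilutes a real association.

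**5. If controls were pooled (equal groups, no association within group).** For a shift of d SD in both variables, |r| = 0.25d²/(1 + 0.25d²):

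- d = 0.5: 0.0625/1.0625 = 0.06
- d = 0.8: 0.16/1.16 = 0.14
- d = 1: 0.25/1.25 = 0.20

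At N = 100 the chance of p<0.05 is 8.9%, 27.7% and 51.5%. If one variable does not differ between groups, r is 0. This case requires the reading that step 1 makes unlikely.

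**6. Cost of a severity term.** The loss of one degree of freedom is trivial: the smallest significant |r| moves from 0.444 to 0.456 at n = 20 and from 0.312 to 0.316 at n = 40. The real cost is the risk in steps 3 and 4, plus a severity grade that the documents do not mention.

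**The case for a change.** The strongest case for a change is that the mechanism comes from the protocol itself and concerns the pair named in the title. A plan should name its analysis sets and covariates, two or three sentences would do it, and reporting torsion-KAM with and without severity would avoid choosing a causal order.

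Part of this stands. No analysis set is attached to each association test, and an unadjusted torsion-KAM coefficient may partly reflect severity. An author who cites it alone as proof that torsion contributes to loading would be overreaching.

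The rest is weaker. The objectives ask about relationships, and the SAP speaks of correlation, predictability and association. A marginal correlation that runs through severity is a real correlation, and the percentages in step 2 are then power to detect it. They become false-positive rates only if the coefficient is read as independent of severity. A severity-adjusted cross-sectional coefficient would not establish a contributor either. For the multiple regression, severity is not named, which is different from being excluded. Finally, the background sentences concern progression over time, so a spread of severity at the visit is itself an assumption.

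**Conclusion.** No change to the plan is called for.

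The unstated population is a gap that analysts would fill sensibly. The title, objective 1 and the passive-tension rationale all point to OA-only association tests, and the harm from pooling depends on the opposite reading.

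The missing severity term is a fair trade-off. Under assumed severity correlations of 0.2, 0.3 and 0.5, omission would shift r by -0.04, -0.09 and -0.25 if severity is a common cause. Inclusion would shift it by +0.04, +0.10 and +0.33 if severity is a consequence of both variables. The protocol's own account, with loading ahead of progression, leans away from adjustment, and the documents give nothing from which to estimate the true size. Reporting both estimates would be a reasonable sensitivity analysis if a severity grade happens to be recorded, but no demonstrated error requires it.

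This rests on the OA-only reading and on taking the objectives at their word as questions of association. What remains is care in wording the results: a cross-sectional coefficient describes an association.
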